1 INTRODUCTION

1.1 Background

Protocol MDGH-MOX-2002 is a Phase 2, multi-center, placebo-controlled, double-blind, randomized dose ranging study to evaluate the efficacy and safety of orally administered moxidectin in adults with scabies.

This Statistical Analysis Plan (SAP) specifies the planned analyses designed to address the study objectives outlined in clinical study protocol MDGH-MOX-2002 version 3 (including amendments 1 and 2), dated 28 Dec 2023. Where there are discrepancies, this SAP will supersede the statistical methods described in the protocol. This SAP will be finalized prior to unblinding study data for the Day 42 analysis. If the finalized SAP is amended prior to unblinding, amendments will be tracked, documented and a rationale provided for each new version. Deviations/changes from the planned analyses described in this SAP will be identified, with justification, in the appropriate section of the clinical study report. Any analysis performed not prospectively defined in this document will be labeled as post hoc and exploratory.

For further information on study conduct, the reader of this SAP is advised to refer to the protocol and other related documents. The specifications for the Tables, Figures and Listings (TFLs) described in this SAP will be provided in a separate document.

1.2 Changes to Protocol Planned Analyses

The following changes have been made to the planned analyses described in the clinical study protocol MDGH-MOX-2002 Version 3 dated 28 Dec 2023:

- The description of the process for randomization, described under Section 10.1 of the current study protocol, was updated in this SAP Section 5.1. Instead of a unique screening number, a site specific sequential Subject Number was allocated to each subject who provided written informed consent. This Subject Number was used throughout the study to identify the subject. A unique Randomization Number was assigned to the subject upon randomization and this randomization number was only recorded on the Randomization electronic case report form (eCRF) page. Study drug was dispensed according to the Randomization Number, not according to the Subject Number.
- Two additional sensitivity analyses have been included to support the primary efficacy analysis:
 - A Completers Analysis excluding subjects with missing data for the primary endpoint with the exception of subjects exposed to scabicides.
 - An analysis that adjusts for Baseline lesion count as the sole covariate, other than randomized treatment group.
- The protocol states that sensitivity analyses will be conducted to assess the impact of missing data on the results. As such, a tipping point analysis has been included in the SAP.
- A repeat of the primary analysis within each Region will not be conducted due to anticipated small sample size within one of the Regions. However, descriptive analyses of the primary efficacy endpoint stratified by Region will be provided.

- Exploratory pairwise comparisons between each of the moxidectin dose groups have been added.
- For the non-informative missing data, the Complete Cure endpoint may be imputed via a fixed value using the methodology detailed in [Appendix 1](#). Should the missing data due to non-informative reasons be 5% of the total sample size, (approximately 200 subjects), a multiple imputation (MI) approach will be implemented using the methodology detailed in [Appendix 2](#).
- The following additional exploratory endpoints have been included in this SAP that are not otherwise listed in the current study protocol:
 - The Day 28 Complete Cure without regards to pruritus.
 - The proportion of index subjects achieving clearance for each individual component of the Complete Cure endpoint
- Pharmacokinetic (PK) data unblinding and analysis may be performed with the extended safety follow up analysis at Week 16.
- The Pharmacokinetic Analysis Plan described in the current protocol that may have been used to describe population-PK and PK/pharmacodynamic analyses will be replaced by Modelling and Simulation Analysis Plans (MSAP). There will be one MSAP to describe the incorporation of PK data into the moxidectin population-PK model, which will be finalized prior to the Day 42 blind break. Another MSAP will describe the PK/pharmacodynamic analyses and will be finalized after the Day 42 blind break.
- An All Randomized Set and Complete Analysis Set have been defined for the purposes of some descriptive tables or sensitivity analyses.

2 STUDY OVERVIEW

This Phase 2 study is a multinational, multi-center, randomized, double-blind, placebo-controlled efficacy and safety study. This study aims to assess the efficacy of a single oral administration of 8 milligrams (mg), 16 mg, or 32 mg moxidectin in achieving Complete Cure at Day 28. This study also aims to assess the safety of the three strengths of single moxidectin doses in patients aged 18 years and older with scabies.

Approximately 200 index subjects will be randomized in the study across sites in the United States and Latin American regions. Within each region, subjects will be randomized into one of 4 cohorts using an equal allocation ratio for a target of approximately 50 subjects per cohort. The cohorts are:

- Placebo
- Moxidectin 8 mg, single dose
- Moxidectin 16 mg, single dose
- Moxidectin 32 mg, single dose

This study will compare each of the three moxidectin doses to placebo in outpatients aged 18 years and older with scabies without significant comorbidities to assess the efficacy of moxidectin in achieving the primary endpoint of Complete Cure by Day 28. Only one subject will be enrolled per household; where more than one household member is screened for

participation in the study, the enrolled (index) subject will be the youngest eligible member of the household. Complete Cure is defined as a combination of clinical cure (all clinical features of the infestation have resolved) and microscopic or dermatoscopic cure (absence of mites and/or mite products and burrows)

Following randomization and treatment administration of eligible subjects on Day 0, all subjects undergo routine safety follow up on Day 7 and Day 14. Blood samples will be collected on Day 0 at 3 and 10 hours post study drug dose administration for the subjects randomly selected for inclusion in the PK subset. On Day 28, subjects will undergo a thorough full-body clinical and microscopic or dermatoscopic assessment to determine the primary efficacy endpoint, and blood samples will be collected for the subjects in the PK subset, a subset of randomly selected subjects for moxidectin plasma concentration analysis. A complete safety review will also be conducted. If at the Day 28 visit the subject has scabies mites confirmed by microscopy or dermoscopy, or their clinical presentation has significantly worsened from Day 0, the subject will receive standard of care treatment for scabies per local guidelines.

All subjects will return on Day 42 for routine safety follow-up including assessment for adverse events (AEs) and concomitant medications. The final blood sample will be collected from the PK subset on Day 42. Extended safety follow-up will occur for all subjects after Day 42, at a Week 12 and final Week 16 visit.

To meet the study objectives, the final analysis for efficacy, along with the analysis of safety data collected through Day 42, will take place after the last subject has completed the Day 42 visit, and when PK sampling is complete in the PK subset. For the Day 42 analyses, the blind will be broken once data through Day 42 have been cleaned, queries resolved, and the data through Day 42 has been “frozen/locked”. This is further detailed in Section 5.2. The blind break will not be added to the clinical trial database but only applied to the Day 42 analysis files. Neither the individual blind break information (e.g., individual treatment assignments) nor the results will be provided to Investigators, study subjects, the clinical management team, or Medical Monitor involved in day-to-day study operations.

Following their Day 42 visit, all subjects will continue to be monitored for safety through the extended safety follow-up period to Week 16. Once the last subject has completed the extended safety follow-up period at Week 16, safety analyses completed for Day 42 safety data will be updated for data collected during the extended safety period. The operational individuals outlined above along with study subjects will remain blinded until subjects complete this extended safety follow up and the extended safety data has been cleaned and the clinical trial database locked

3 STUDY OBJECTIVES

3.1 Primary Objectives

The primary objectives of the study are:

- To compare the efficacy of a single oral administration of moxidectin for each of the three moxidectin doses to matching placebo with respect to the Day 28 Complete Cure rate.
- To compare the safety of a single oral administration of moxidectin for each of the three moxidectin doses with placebo.

3.2 Secondary Objective

There are no secondary objectives.

3.3 Exploratory Objectives

The exploratory objectives of the study are:

- For each of the three moxidectin doses, determine the Day 28 Complete Cure rate.

In each of the 4 groups determine:

- The Day 28 clinical cure rates,
- The Day 28 combined microscopic and dermatoscopic cure rates,
- The Day 28 Investigator-assessed Cure rates,
- The Day 28 Complete Cure without regards to pruritus,
- The proportion of index subjects achieving clearance for each individual component of the Complete Cure endpoint,
- The concordance between the Complete Cure rate and Investigator-assessed Cure rate,
- The change from Baseline in the total number of lesions at Day 28,

And assess:

- Secondary bacterial infection at Day 28,
- PK of moxidectin in a subset of subjects.

3.4 Estimand

The estimand for each of the primary efficacy hypotheses is the comparison of the Day 28 Complete Cure rate of moxidectin without use of rescue medication versus the Day 28 Complete Cure rate of placebo without use of rescue medication.

The summary of the estimand is shown in [Table 1](#).

Table 1: Summary of Estimand for the Primary Endpoint

Primary Endpoint	Population	Intercurrent event(s)	Handling of Missing Data	Population-Level Summary
The primary efficacy endpoint is the proportion of index subjects achieving Complete Cure at Day 28.	
The Full Analysis Set (FAS) will be the primary analysis set for the primary and, unless otherwise stated, all other efficacy analyses.
 
The FAS is defined as all randomized index subjects receiving study drug.
 
Subjects in the FAS will be analyzed according to the treatment group to which they were randomized.
	Index subjects exposed to scabicides prior to Day 28 will be imputed as a non-responder	
Informative missing will be imputed as non-responders.
 
Non-informative missing will be imputed as a non-responder or a responder using either:
 
fixed imputation logistic regression model 
or
 
multiple imputation if the number of subjects with non-informative missing data is greater than 5% of the total sample size	Marginal Risk Difference for each of 3 moxidectin dose groups versus placebo adjusted for region (United States or Latin America).

4 SAMPLE SIZE DETERMINATION

Approximately 200 index subjects will be randomized into one of four cohorts using an equal allocation ratio. Only one subject will be enrolled per household; where more than one household member is screened for the study, the index subject is the youngest eligible member of the household.

The target sample sizes per randomized treatment group are shown in [Table 2](#). The sample size was selected to address the study's primary efficacy objective.

Table 2: Sample Size by Randomized Treatment Group

Randomized Treatment Group	Target Sample Size
Placebo	N = 50
Moxidectin 8 mg, single dose	N = 50
Moxidectin 16 mg, single dose	N = 50
Moxidectin 32 mg, single dose	N = 50

A sample size of 50 subjects per randomized treatment group will yield an approximate power of 75% for the pairwise comparisons of each moxidectin dose group to placebo assuming a placebo Day 28 Complete Cure rate of 40% or less and a moxidectin Day 28 Complete Cure rate of 70% or more. Power calculations for each pairwise comparison were conducted via a Z test for two independent proportions with pooled variance at a two-tailed adjusted alpha of 0.019. The pairwise adjusted alpha of 0.019 is used to control the familywise error rate (FWER) at an overall two-tailed alpha of 0.05 using a large sample approximation to Dunnett's critical value for the 3 pairwise comparisons of each moxidectin dose group to placebo.

5 RANDOMIZATION AND BLINDING

5.1 Randomization

A unique subject number was allocated to each subject who provided written informed consent. The subject number was allocated sequentially by site. Subjects who failed screening and were approved to be rescreened retained their original subject number.

On Day 0, eligibility was reconfirmed prior to subject randomization using an Interactive Response Technology (IRT) system when each subject was assigned a unique randomization number.

Within the IRT system, the randomization of subjects to treatment is stratified by region (United States [US] and Latin America). Within each region, a permuted block randomization algorithm reflecting an equal allocation ratio among the 4 treatment cohorts of 1:1:1:1 was derived. The algorithm within each region was independent and may consist of randomly varying block sizes. Block sizes were not revealed to sites or Sponsor personnel involved in the conduct of the study. The algorithm was generated by an unblinded statistician who was otherwise independent of the study at the time the code was generated.

A subset of approximately 20 subjects will be randomly selected from each arm to provide sparse blood samples for PK analyses. To ensure the study drug allocation remains blinded, subjects from all arms of the study will be sampled.

5.2 Blinding

Clinic staff, subjects, operational Sponsor personnel and delegates were blinded as to which treatment each subject received until the last subject had completed their Week 16 visit. To maintain the blind, each subject received the same number of capsules, regardless of dose. Any break of the study blind, inadvertent or otherwise, was to be reported to the Sponsor without revealing the actual treatment assignment, as soon as possible. The site nominated an unblinded pharmacist to dispense the investigational medication per the randomization received from the IRT system.

Once all subjects have completed the Day 42 visit, the final analysis of efficacy and safety data collected through Day 42 will be conducted. For these analyses, the blind will be broken once data through Day 42 have been cleaned, queries resolved, and the data through Day 42 has been “frozen/locked”. The blind break will not be added to the clinical trial database but only applied to the Day 42 analysis files. Neither the individual blind break information (e.g., individual treatment assignments) nor the results will be provided to Investigators, study subjects, the clinical management team, or Medical Monitor involved in day-to-day study operations. These individuals will remain blinded until subjects complete the extended safety follow up with the Week 16 visit and the extended safety data has been cleaned and the clinical trial database locked.

Members of the Moxidectin for Scabies Project Team may be unblinded at the Day 42 database lock point but will not be involved in oversight of post-Day 42 individual subject data. Details of study personnel who will be unblinded or remain blinded will be captured in a separate document to this SAP.

6 STUDY ENDPOINTS

6.1 Primary Efficacy Endpoint

The primary efficacy endpoint is the proportion of index subjects achieving Complete Cure at Day 28. Complete Cure is defined as demonstration of both:

(1) Clinical cure (all signs and symptoms have completely resolved, including burrows, inflammatory/noninflammatory lesions and pruritus).

and

(2) Microscopic or dermatoscopic cure demonstrating the absence of mites, eggs, and/or scybala, and negative dermoscopy for burrows.

Complete Cure will be derived from the individual assessments captured on the Day 28 Scabies Assessment eCRF page where:

- Lesion count is 0, and,
- Pruritus is ‘Absent’, and,
- Mites are ‘Absent’, and,
- Eggs are ‘Absent’, and,
- Scybala are ‘Absent’, and,
- Burrows (by dermoscopy) are ‘Absent’.

An index subject will be considered as having achieved Complete Cure at Day 28 if all of the 6 components are either 0 or “Absent” as specified above. If any of the 6 components are missing, whether because the individual component is missed or because the Day 28 visit was missed, the Complete Cure endpoint at Day 28 will be considered missing and the subject will be imputed as a non-responder (not cured). An exception will be made if the missed visit is non-informative. See Section 9.11.2 for further detail on handling missing data for the Day 28 Complete Cure endpoint.

The Day 28 Complete Cure endpoint for subjects exposed to scabicides prior to their Day 28 assessment will also be imputed as a non-responder (not cured). Scabicides are defined as any scabicide, including permethrin, ivermectin, benzyl benzoate, sulfur, lindane, crotamiton, malathion, tea tree oil, or spinosad used between Day 0 and Day 28. Scabicides do not include products used to manage the symptoms of scabies. Subjects exposed to scabicides as concomitant medications with unknown start dates will also be imputed as non-responders, unless the end date is known and after Day 28.

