9.4.9 Scabies Assessments

At Screening, active scabies infestation will be confirmed by the presence of clinical signs and symptoms (evidence of burrows, typical inflammatory/noninflammatory lesions) as well as microscopic examination of skin scrapings or dermoscopy to demonstrate the presence of scabies mite(s), eggs and/or scybala. At Screening, dermoscopy is the preferred methodology for identification of mites, eggs, and/or scybala and to confirm the presence of burrows in the skin.

On Day 0 (prior to randomization) and on Day 28, subjects will be assessed for the presence of scabies mites, eggs, scybala, burrows, inflammatory/noninflammatory lesions and pruritus. Apart from burrows, primary and secondary signs of scabies infestation visible on the skin can include papules, vesicles, nodules, erythema, and excoriations.

The procedure for conducting scabies assessments on Day 0 and Day 28 is:

- Signs and symptoms of scabies infestation will be mapped according to pre-specified anatomical body regions.
- The presence or absence of mites, eggs or scybala will be confirmed by either microscopy of material taken from the skin via skin scraping, or by dermoscopy. If skin scraping is performed, material should be collected from skin showing burrows or lesions or from previously affected sites if signs have resolved. The method used, whether microscopy or dermoscopy, will be recorded in the subject's source notes and CRF.
- Dermoscopy will be used to confirm the presence or absence of burrows,
- Lesions will be counted, and nodules noted if present,
- Subjects will be reviewed for evidence of pruritus,
- Secondary bacterial infections will be noted if present (note that secondary bacterial infections are not included in the assessment of Complete Cure).

Separately, an Investigator Assessment of Cure will also be completed at Day 28. Based on the subject's clinical presentation, the Investigator will determine whether:

- The scabies infestation is clear with all signs resolved,
- The scabies infestation is clear with incomplete resolution of signs, and no additional treatment with standard of care is warranted,
- The scabies infestation is not clear and additional treatment with standard of care is warranted.

These data will be recorded in the subject's study records and CRF.

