8.5 Complete Analysis Set

The Complete Analysis Set will include all FAS subjects, except those FAS subjects exposed to scabicides prior to Day 28 and any FAS subject with a missing Day 28 Complete Cure assessment (including if any of the individual components of the Complete Cure endpoint is missing).

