9.6 Protocol Deviations

A blinded review of protocol deviations documented during the study will be completed prior to the database freeze/lock and blind break for the Day 42 analysis. Protocol deviations are categorized at the time of entry into the Protocol Deviation eCRF page, but categorization will be reviewed during blinded review of all protocol deviations, and they will also be classified as major/minor:

- Consent procedures
- Inclusion/exclusion criteria
- Randomization procedures

- Concomitant medication/therapy
- Study procedures
- Serious adverse event (SAE) reporting
- Dosing
- Unblinding
- Scabies Assessment outside the Day 28 Visit Window
- Other Visit schedule/ interval
- COVID-19 related
- Other

Major protocol deviations will be defined as deviations that could potentially have a meaningful impact on the efficacy or safety results. Subjects with major protocol deviations that might impact efficacy will be excluded from the PPAS.

Some categories of major protocol deviations that might be considered as having a meaningful impact on the efficacy results include but are not limited to:

- Subjects failing any eligibility criteria,
- Subjects with treatment administration errors,
- Subjects randomized but not exposed to study drug (exclusion from FAS, PPAS, SfAS), and PK,
- Significant non-compliance with specified study visits windows,
- Administration of scabicides prior to the Day 28 visit (note: the exposure to scabicides prior to Day 28 is considered a major protocol deviation and subjects will be considered non-responders for the primary analysis)

Protocol deviations leading to missing data will also be reviewed to assess the reasons why the data are missing and whether they are considered informative or non-informative reasons for the purposes of handling of missing data described in Section 9.11.2. Where the reason(s) for missing data is unknown and/or not fully documented, the default will be to assume informative missing. Examples of non-informative missing data might be:

- Missed visit due to weather, travel, or childcare,
- Missed visit due to COVID-19 or COVID-19 exposure,
- Missed assessment due to equipment failure.

All determinations of informative and non-informative missing data will be fully documented and reported.

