As supportive analyses, the Day 28 Complete Cure rates for each moxidectin group and placebo, as well as the risk difference and 95% CIs for each pairwise comparison, will be calculated within each region. For these region subgroup analyses the proportion of index subjects achieving a Day 28 Complete cure for each randomized treatment group within region will be the unadjusted proportions with Wald 95% CIs for a single proportion. The 95% CI for the risk difference will be the Wald CIs for the difference between two independent proportions using the unpooled variance. Any significance test of the risk difference conducted within region will

be viewed as supportive and exploratory due to the potential lack of power. The 95% CIs and any hypothesis tests for these supportive analyses will not be adjusted for multiplicity.

See [Appendix 3](#) for specification of the logistic model and bootstrapping.

9.11.2 Handling of Missing Data for the Primary Analysis of Day 28 Complete Cure

For the Day 28 Complete Cure endpoint, subjects exposed to rescue medication (scabicides, including permethrin, ivermectin, benzyl benzoate, sulfur, lindane, crotamiton, malathion, tea tree oil, or spinosad) prior to the Day 28 assessment will be imputed as a non-responder. If a subject is exposed to a scabicide as a concomitant medication with an unknown start date, they will also be imputed as a non-responder unless the end date is known and is after Day 28. Additionally, subjects with missing Day 28 Complete Cure assessments due to missed visits or incomplete scabies assessments at Day 28 will also be imputed as non-responders. An exception would be if the missing Complete Cure endpoint was missing for reasons deemed as non-informative i.e. the Day 28 visit was missed because weather conditions prevented travel. For the non-informative missing data, the Complete Cure endpoint may be imputed via a fixed value using the methodology detailed in [Appendix 1](#). Should the missing data due to non-informative reasons be greater than 5% of the total sample size (approximately 200 subjects), a multiple imputation approach will be implemented, see [Appendix 2](#).

The determination of the use of rescue medication as well as informative vs non-informative missing data will be conducted prior to the blind break for the Day 42 analysis, see Section [9.6](#).

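### The SAP lets a missing component override an observed positive one, so an attending subject already shown not cured at Day 28 can be imputed as cured

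*SAP*

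**What the plan says.** SAP 6.1 requires all six Day 28 components to be clear: lesion count, pruritus, mites, eggs, scybala, and burrows by dermoscopy. For incomplete data it sets this trigger: "If any of the 6 components are missing, whether because the individual component is missed or because the Day 28 visit was missed". The consequence it attaches to that trigger is that "the Complete Cure endpoint at Day 28 will be considered missing and the subject will be imputed as a non-responder (not cured"). Its only exception is "An exception will be made if the missed visit is non-informative", and it points to 9.11.2 for detail.

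SAP 9.11.2 repeats the default for endpoints missing "due to missed visits or incomplete scabies assessments at Day 28 will also be imputed as non-responders". It then words the exception more broadly: "An exception would be if the missing Complete Cure endpoint was missing for reasons deemed as non-informative". The illustration it gives is a visit missed because of weather.

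SAP 9.6 lists possible non-informative reasons, one of which is "Missed assessment due to equipment failure". Where the reason is unknown or not fully documented, the default is informative.

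Non-informative cases go to Appendix 1, or to the multiple imputation in Appendix 2 if they exceed 5% of about 200 subjects. Appendix 1 fits one logistic model and scores a subject as cured when the predicted probability is above 0.50. Appendix 2 imputes within each arm. The predictors are region, demographics, scabies history and baseline findings, plus treatment arm in Appendix 1.

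The Complete Analysis Set (8.5) drops subjects with a missing endpoint, "including if any of the individual components of the Complete Cure endpoint is missing". The tipping-point analysis (9.11.3.2) leaves non-informative imputations unchanged.

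**The concern.** The six components are joined by AND. One observed positive component settles the outcome as not cured, whatever the missing ones would have shown. The SAP has no rule saying so. It classes the subject as missing first and then decides how to impute.

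Partial assessment is a realistic case. Protocol 9.4.9 says "Dermoscopy will be used to confirm the presence or absence of burrows", whereas mites, eggs and scybala may be checked by microscopy, and no device is named for the lesion count or pruritus review. A failed dermatoscope can therefore leave up to five components recorded and burrows missing.

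At stake is the derivation of the only primary efficacy endpoint. A listing could show a subject with recorded lesions or mites analysed as cured. Two programmers could also derive different endpoints, depending on whether they followed 6.1 or 9.11.2.

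**Working it through.** **1. Tracing one subject.** Suppose a subject attends Day 28 with 15 lesions and pruritus present, but burrows are not recorded because the dermatoscope failed.

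| Step | Result |
|---|---|
| Definition of Complete Cure (6.1) | Not cured; already decided |
| Missing-component rule (6.1) | Endpoint missing; default non-responder |
| Exception in 6.1 | Does not apply, because the visit was not missed |
| 9.6 | Equipment failure may be judged non-informative |
| Exception in 9.11.2 | Applies; subject goes to Appendix 1 or 2 |
| Appendix 1 or 2 | No Day 28 component used; cured is possible |
| 9.11.3.2 and 8.5 | Imputed value held fixed; subject dropped from the Complete Analysis Set |

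Under 6.1 alone the answer is right. Under 9.11.2 with 9.6 it can be wrong.

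**2. The plan's own figure.** Inputs from SAP 4: n = 50 per arm, 40% vs 70%, two-tailed alpha 0.019 (z = 2.346), pooled Z-test.

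Power = Φ[(0.30 − 2.346 × √(2 × 0.55 × 0.45/50)) / √((0.24 + 0.21)/50)] = Φ(0.0666/0.0949) ≈ 0.759. The stated figure of about 75% reproduces. The large-sample Dunnett value for three comparisons is 2.349, two-tailed alpha 0.0188, which rounds to 0.019.

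**3. Effect of one subject.** 1/50 = 0.02, or 2 points on that arm's rate and on its risk difference.

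**4. Expected effect under Appendix 1.** The documents give no rate of partial assessment. Assume 10 partly assessed subjects with a non-informative reason. That is the most Appendix 1 can receive (0.05 × 200 = 10), or 2.5 per arm if spread evenly. At the design rates, true failures among them are:

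- moxidectin arm: 2.5 × 0.30 = 0.75
- placebo arm: 2.5 × 0.60 = 1.50

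*Outer range.* Suppose every moxidectin failure is imputed cured, no placebo failure is, and between 0 and 100% of failures have a recorded positive component. Bias = 0 to 0.75/50 = 0 to 0.015.

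*With imputation shares.* In simulations of Appendix 1 at 70%/40% with 50 per arm and weakly prognostic covariates, about 92% of missing moxidectin subjects and 25% of placebo subjects were imputed cured. If every failure shows a recorded positive:

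(0.75 × 0.92 − 1.50 × 0.25)/50 = 0.315/50 = +0.006, or about +0.6 points.

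The shares depend on covariate strength, which is assumed. Across a range from no to fairly strong prognostic value, 62 to 94% of true moxidectin failures and 20 to 24% of true placebo failures were imputed cured. The extreme pairings give (0.75 × 0.62 − 1.50 × 0.24)/50 = +0.2 points and (0.75 × 0.94 − 1.50 × 0.20)/50 = +0.8 points.

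**5. Expected effect under Appendix 2.** Imputing within arm at the arm's own rate, the expected flips per partly assessed subject are 0.30 × 0.70 = 0.21 on moxidectin and 0.60 × 0.40 = 0.24 on placebo. The net effect is slightly against moxidectin.

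**6. A borderline result.** Using the SAP's fallback pooled Z-test with placebo at 20/50:

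| Moxidectin | Risk difference | Z | p | Below 0.019? |
|---|---|---|---|---|
| 31/50 | 0.22 | 2.20 | 0.028 | No |
| 32/50 | 0.24 | 2.40 | 0.016 | Yes |

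If exactly one moxidectin failure is flipped and no placebo failure is, the exact probability of a significant result favouring moxidectin rises from 0.38 to 0.46 at true rates of 60% vs 40%, and from 0.77 to 0.83 at 70% vs 40%.

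**The case against.** The strongest reply is that 6.1 already gives the right answer. It imputes non-responder, and its exception covers only a missed visit. The broader route rests on 9.11.2, whose sole illustration is also a missed visit, and on one tentative example in 9.6 that does not say other components were recorded as positive. Undocumented reasons default to informative. The calls are made before the blind break and documented, and every imputed subject is listed with the reason. Errors would be few and visible.

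Much of this stands. It limits the number of cases and guards against selective classification. It does not close the route: 6.1 defers to 9.11.2, whose exception follows directly after incomplete assessments are named, and the 9.6 example is a missed assessment, not a missed visit. A listing shows the error but does not correct it.

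A reader might infer that one device failure would affect a whole clinic day of subjects. The protocol's figures do not support that. About 200 subjects at 8 to 20 sites over about 6 months (26 weeks) is 200/(8 × 26) ≈ 1.0 down to 200/(20 × 26) ≈ 0.4 Day 28 visits per site per week. The −2/+4 day window may also allow a repeat check.

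Dropping partly assessed subjects from the Complete Analysis Set follows its stated definition, and it is only a sensitivity set. That part of the point is secondary.

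**Conclusion.** The point holds as a gap in the derivation rule and a mismatch between sections. As written, SAP 6.1, 9.6 and 9.11.2 together allow an observed failure to be analysed as cured, and neither the tipping-point nor the Complete Analysis Set analysis would score it as a failure.

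The expected bias in the risk difference is about 0 to 1.5 points, and about +0.6 for ten partly assessed subjects spread evenly under Appendix 1. This rests on the design cure rates, an assumed number of such subjects, and assumed covariate strength. Planned power is unaffected. One subject can still decide a borderline comparison.

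Two stronger readings are not supported:

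- **A bias near 2.7 points.** This follows from 2/50 × (0.92 − 0.25), which needs two known failures in every arm and weakly prognostic covariates. At the design rates placebo has twice as many failures as moxidectin, which offsets much of the difference.
- **A systematic lean towards moxidectin.** Appendix 1 tends that way because of its 0.50 cut-off. Appendix 2 does not.

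Severity is minor to moderate. It is worth correcting because it concerns the sole primary efficacy endpoint and the correction is cheap.

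**What to change.** Before the Day 42 blind break:

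1. **SAP 6.1.** State that any observed positive component (lesion count above 0, or pruritus, mites, eggs, scybala or burrows present) means not cured, whatever else is missing. The endpoint is missing only if every recorded component is clear and at least one is missing.
2. **SAP 6.1, 9.6 and 9.11.2.** Use one wording for the exception, and say whether it covers missed visits only or also incomplete assessments.
3. **Partly assessed, all-clear subjects.** Either keep the 6.1 non-responder default or impute conditionally on the components observed clear. Do not use the baseline-only model. Once observed failures are scored as such, that model would understate cure. If components are missing at random and every failure shows a recorded positive, Appendix 2 would give partly assessed subjects a cure rate of 0.70 × 0.70 = 49% on moxidectin against a true 70%, and 0.40 × 0.40 = 16% on placebo against 40%. The non-responder default is simpler but conservative: with 2.5 such subjects per arm it lowers the risk difference by 2.5 × (0.70 − 0.40)/50 = 1.5 points.
4. **SAP 8.5.** Apply rule 1, so that observed failures stay in the Complete Analysis Set.

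Items 1, 2 and 4 take a few sentences and a line of derivation code. Item 3 needs a decision and, if conditional imputation is chosen, a short specification. Sample size and planned power do not change.
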